# **List of Abbreviations**

IRB	Institutional Review Board	
LAR	Legally Authorized Representative	
PII	Personally Identifiable Information	
TLS	Transport Layer Security	
CDC	Centers for Disease Control and Prevention	
ePRO	Electronic Patient Reported Outcomes	
RCT	Randomized Controlled Trial	
CVD-I	Cardiovascular disease-intervention	
CVD-C	Cardiovascular disease-control	

Version 1 4 of 22

# **Statement of Compliance**

The protocol, Data Usage Agreement & Permissions form, recruitment materials, and all participant materials will be submitted to the Solutions Institutional Review Board for review and approval. Approval of both the protocol and the Data Usage Agreement & Permissions form must be obtained before any participant is enrolled. Any amendment to the protocol or Data Usage Agreement & Permissions form will require review and approval by Solutions IRB before the changes are implemented to the study. A determination will be made regarding whether a new Data Usage Agreement & Permissions form needs to be obtained from participants who provided agreement to participate using a previously approved Data Usage Agreement & Permissions form.

# **Protocol Summary**

Title	Increasing Influenza Vaccination in Individuals with Cardiovascular Conditions: Assessing the Effectiveness of a Digital Intervention in a Decentralized Randomized Controlled Trial			
Study Design	A 6-month prospective, digital randomized controlled trial targeting approximately 35,000 individuals to evaluate the effectiveness of an influenza vaccination intervention during influenza season for people with cardiovascular conditions			
Objectives	Primary:  To determine the effectiveness of a digital intervention designed to increase influenza vaccination rates in individuals with cardiovascular disease (CVD) by examining:  • Differences in self-reported influenza vaccination rates between individuals with cardiovascular disease who receive a targeted digital intervention (CVD-I) aimed at increasing influenza vaccination and those with cardiovascular disease who received no intervention (CVD-C) by the end of the study period  Secondary:  1) To examine differences in vaccination rates between individuals in the intervention group who engaged with different numbers of intervention messages, and changes in self-reported vaccination rates following intervention messages			

Version 1 5 of 22

- 2) To describe levels of engagement with the intervention messages and perceptions of the intervention messages within the CVD-I group
- To examine predictors of vaccination status, including cardiovascular condition type, vaccine drivers/barriers, and vaccine knowledge, across diagnoses and within CVD-I and CVD-C groups

### Exploratory:

- 1) To examine the potential impact of COVID-19 pandemic on influenza vaccination rates
- To describe self-reported complications from influenza experienced by individuals with different cardiovascular conditions during the 6-month study period, as well as differences in complications by vaccination status
- 3) To examine differences in wearable data (e.g., sleep, steps, heart rate) between individuals who experience self-reported influenza and those who do not, as well as differences in wearable data between cardiovascular conditions

#### **Endpoints**

#### Primary endpoint

Self-reported influenza vaccination rates

#### Secondary endpoints

- Engagement with interventions (i.e., clicking, opening, completing)
- Self-reported vaccine drivers/barriers, and vaccine knowledge

#### **Exploratory endpoints**

- Self-reported impact of COVID-19 on influenza vaccination behavior
- Self-reported complications from influenza
- Passively collected wearable data (e.g., sleep, steps, heart rate)

Version 1 6 of 22

### **Patient Population**

#### Inclusion Criteria:

- Age 18 years or older
- Resides in the U.S.
- Speaks, reads, and understands English
- Has self-reported being diagnosed with any of the following cardiac conditions below in their Achievement profile:
  - o Atrial Fibrillation or Afib
  - Abnormal or irregular heart rhythm, other arrhythmic heart disease
  - Cardiac arrest, or heart attack (myocardial infarction)
  - Coronary heart disease like a heart blockage, treated with medications, a stent in the heart, or sometimes bypass surgery
  - Heart failure, like congestive heart failure
  - Stroke or cerebrovascular accident (CVA)

#### **Exclusion Criteria:**

 Participated in Step 1, Part 2 semi-structured interviews used to obtain feedback on the intervention messages

Version 1 7 of 22

### 1. Introduction

#### 1.1. Overview of Therapy Area

Influenza impacts approximately 5-20% of the population of the United States annually, resulting in significant economic impact and public health burden (Molinari et al., 2007). For people with cardiovascular conditions, influenza can be particularly burdensome, thus they are considered a high-risk group (CDC, 2019). Vaccination for influenza remains the most effective primary prevention method against influenza, with effectiveness ranging from 38-48% in the past few years (Centers for Disease Control and Prevention (CDC), 2018; Dos Santos, Tahrat, & Bekkat-Berkani, 2018; Doyle, 2019; Jackson et al., 2017; Rolfes et al., 2019). The CDC reports that the vaccination rate in the 2018-2019 season was 47.9% for individuals 18-64 years of age who have high risk conditions such as cardiovascular conditions (CDC, 2019). While this is higher than the rate of 36.4% in same age individuals without high risk conditions, it is far below the 70% national vaccination rate goal (Healthy People 2020, 2019). Given the increased burden that influenza represents for people with high risk conditions, even small improvements in vaccination rates could result in significant impact and provide benefit to patients, healthcare providers, and insurance payors (Molinari et al., 2007).

### 1.2. Study Rationale

To date, there are no large-scale RCTs on digital interventions for increasing vaccination rates in people with cardiovascular conditions. One observational study has demonstrated the potential effectiveness of general messaging and incentives via a health-related app to increase vaccine uptake in the general Canadian population (Dale, White, Mitchell, & Faulkner, 2019), suggesting this kind of intervention could be effective with people with cardiovascular conditions. In a separate study, a large randomized controlled trial (RCT) using digital messaging with incentives to vaccinate was found to be effective in increasing vaccination rates in a general population of adults in the United States (Lee et al., 2020). Of particular interest is a digital RCT in a sample of individuals with diabetes, a population with increased risk of influenza-related complications, that used digital messaging and was found to be effective in increasing vaccination rates (Samson, et al., 2020). An additional study of individuals with diabetes that was a collaboration between Sanofi Pasteur and Evidation also demonstrated the impact of influenza and related complications on data retrieved from wearables; showing that people who developed influenza engaged in less activity around the time of diagnosis and recorded an increased heart rate, a unique passive marker of infection (Samson et al., 2019). These studies all suggest that the development of a digital intervention targeted to individuals with cardiovascular conditions could be beneficial in increasing vaccination rates.

#### 1.3. Intervention Overview

Version 1 8 of 22

The digital intervention messages were developed using a 3-part approach: 1) a quantitative assessment of more than 800 patient perspectives for people with cardiovascular disorders, assessing their behaviors, thoughts, and beliefs surrounding vaccination; 2) semi-structured interviews with approximately 25 patients who had cardiovascular diseases to gather their perspectives and feedback on proposed intervention messages; and 3) an expert panel of cardiologists, behavioral scientists, and vaccine policy experts for expert input on content and accuracy of scientific information provided. This approach to intervention development was consistent with the Patient Centered Outcomes Research Institute (PCORI) recommendation for developing interventions that increase participant recruitment and retention, improve patient outcomes, and increase research validity and relevance to the real world (Frank, Basch, & Selby, 2014). The intervention messages provide informational content on the influenza vaccine (sourced from the Centers for Disease Control and Prevention and the American Heart Association), specific information about influenza and cardiovascular disorders, and behavioral prompts (e.g., reminders) surrounding influenza vaccination behaviors.

# 2. Study Objectives

#### 2.1. Primary Objective

• To determine the effectiveness of a digital intervention designed to increase influenza vaccination rates in individuals with cardiovascular diagnoses (CV diagnoses) by examining differences in self-reported influenza vaccination rates between individuals with cardiovascular disease who receive a targeted digital intervention (CVD-I) aimed at increasing influenza vaccination and those with CV diagnoses who received no intervention (CVD-C) by the end of the study period.

#### 2.2. Secondary Objectives

- To examine differences in vaccination rates between individuals in CVD-I who engaged with different numbers of intervention messages, and changes in self-reported vaccination rates following intervention messages
- To describe levels of engagement with the intervention messages and perceptions of the intervention messages within the CVD-I group
- To examine predictors of vaccination status, including cardiovascular condition type, vaccine drivers/barriers, and vaccine knowledge, across diagnoses and within CVD-I and CVD-C groups

#### 2.3 Exploratory Objectives

• To examine the potential impact of COVID-19 pandemic on vaccination rates

Version 1 9 of 22

- To describe self-reported complications from influenza experienced by individuals with different cardiovascular conditions during the 6-month study period, as well as differences in complications by vaccination status
- To examine differences in wearable data (e.g., sleep, steps, heart rate) between individuals who experience self-reported influenza and those who do not, as well as differences in wearable data between cardiovascular conditions

### 3. Study Design

### 3.1. Overall Design

- A 6-month prospective, digital randomized controlled trial targeting approximately 35,000 individuals to evaluate the effectiveness of an influenza vaccination intervention during influenza season for people with cardiovascular conditions
- Two study arms: cardiovascular disorders digital intervention arm (CVD-I) & cardiovascular disorders without digital intervention arm (control: CVD-C)

### 4. Study Endpoints

#### 4.1. Primary Endpoint

The primary endpoint in this study is to examine differences in self-reported influenza vaccination rates between individuals with cardiovascular disease who receive a targeted digital intervention (CVD-I) aimed at increasing influenza vaccination and those with cardiovascular disease who received no intervention (CVD-C).

#### 4.2. Secondary Endpoint

The secondary endpoints in this study are:

- To examine predictors of vaccination status, including cardiovascular condition type, vaccine drivers/barriers, and vaccine knowledge, across and between CVD-I and CVD-C.
- Engagement with interventions, including clicking, opening, or completing the intervention messages

#### 4.3. Exploratory Endpoints

The exploratory endpoints in this study include:

 To describe the self-reported impact of the COVID-19 pandemic on influenza vaccination behavior

Version 1 10 of 22

- To describe self-reported complications from influenza experienced by individuals with different cardiovascular conditions during the 6-month study period, as well as differences in complications by vaccination status.
- To examine differences in wearable data (i.e., sleep, steps, heart rate) between individuals who experience influenza and those who do not, as well as differences in wearable data between cardiovascular conditions.

# 5. Study Population

#### 5.1. Inclusion and Exclusion Criteria

Inclusion Criteria	Exclusion Criteria

 
Age 18 years or older
 
Resides in the U.S.
 
Speaks, reads, and understands English
 
Has self-reported being diagnosed with any of the following cardiac conditions below in their Achievement profile: 
 
Atrial Fibrillation or Afib
 
Abnormal or irregular heart rhythm, other arrhythmic heart disease
 
Cardiac arrest, or heart attack (myocardial infarction)
 
Coronary heart disease like a heart blockage, treated with medications, a stent in the heart, or sometimes bypass surgery
 
Heart failure, like congestive heart failure
 
Stroke or cerebrovascular accident (CVA)
 
 
 
	Participated in Step 1, Part 2 semi-structured interviews used to obtain feedback on the intervention messages.

#### 5.2. Recruitment Methods

Achievement, a product of Evidation Health, is an online platform where people can connect their digital health tools, including wearable activity trackers and fitness apps. Achievement

Version 1 11 of 22

members agree to being contacted with study opportunities when they create an Achievement account. Evidation Health will leverage Achievement for recruitment, and will use an online strategy and study platform to develop a target list of participants, verify eligibility, and enroll participants into this study.

A set of existing Achievement members who have previously self-reported to meeting the inclusion criteria will be tagged for study inclusion, termed "participants" from here on. Since participants will be blinded to their study participation status, participants will not be asked to take any action to enroll in the study. In order to identify a target list of participants, Evidation Health will leverage already permissioned information from Achievement members, including data on their cardiovascular diagnoses, age, sex/gender, race/ethnicity, and country of residence. These participants will be randomized using block randomization into CVD-Intervention or CVD-Control prior to being offered the opportunity to complete any study activities. Randomization will ensure that the groups are representative of the general Achievement population with cardiovascular disease. Efforts will be made to target individuals for enrollment who identify as being of a race/ethnicity that is something other than non-Hispanic White, as well as representative in sex/gender. Participants will be sent offers via the Achievement platform to complete study activities. Participants can complete any number of survey activities (demographics, baseline, 3-month survey, and/or 6-month survey, intervention messages); completion of intervention activities will not be required for enrollment for the CVD-I group.

### 6. Study Procedures

#### 6.1. Study Enrollment

Participants will be sent offers on the Achievement Studies Platform to complete study activities. Participants can complete any number of survey activities (baseline, 3-month survey, and/or 6-month survey, intervention messages); completion of intervention activities will not be required for enrollment for the CVD-I group.

#### 6.2. Informed Consent

We will request that informed consent is exempt for this study for the following reasons:

- Participation in this study involves no more than minimal risk to the privacy of individuals.
- Given the nature of the study, which aims to measure influenza vaccination rates in a
  real-world setting, priming the participants with a consent form will likely alter the
  perception of the interventions and may impact how individuals respond to the study
  assessments, potentially biasing the results and limiting the generalizability of the
  findings. For this reason, this study could not be practically carried out without the
  waiver of informed consent.
- At the beginning of each questionnaire, participants will be notified on how their survey responses and behavioral data will be used for research purposes via a Data Usage & Permissions Agreement.

Version 1 12 of 22

#### 6.3. Study Steps

Participants will be sent an offer to complete a survey at baseline, 3 months, and 6 months. A separate demographic and medical history survey will remain available for participants to complete throughout the study. Additional information on study experiences and intervention feedback will be gathered in the 6-month survey for those in the CVD-I group. Data from an activity tracker will be collected if one is already connected to the participant's Achievement account, consistent with their completion of the Data Usage & Permissions Agreement. Activity tracker data will be collected retrospectively and prospectively. Participants in the CVD-I arm only will be sent intervention messages on predetermined days for the duration of the 6-month study intervention period. At the end of the intervention period, individuals who completed a data usage and permissions agreement as a part of the surveys will be informed via email that the survey information they contributed was for a research study investigating influenza vaccination behavior in people with cardiovascular conditions.

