#### 7. **Data Types and Outcomes**

- Data from self-reported survey:
  - Demographics
  - Medical history
  - Health behaviors
  - Healthcare utilization
  - Influenza vaccination status, experience, and complications
  - COVID-19 experiences
  - Vaccine attitudes and barriers
  - Influenza risks and healthcare provider role
  - Experience and perceptions of intervention materials (CVD-I only)
- Data from engagement with interventions (CVD-I only)
  - For example, clicks, dismissals, or completions of interventions
- Data from Achievement Profile
  - Activity data generated by wearables (e.g., heart rate, sleep, step data), from 12 months before participation and 12 months after participation (if available)

	Source	Retrospective	Demographics	Baseline	Month 3	Month 6
--	--------	---------------	--------------	----------	---------	---------

Version 1 14 of 22

		12 months before to 12 months after	Survey			
Self-reported data						
Demographics	Survey		X			
Medical history	Survey		X			
Health behavior history & influenza vaccination	Survey		X			
Healthcare utilization	Survey			X	X	X
Influenza vaccination status	Survey			X	X	X
Influenza experience & complications	Survey			X	X	X
COVID-19 experiences & perceptions	Survey			X	X	X
Vaccine drivers & barriers	Survey			X	X	X
Influenza risks & healthcare provider role	Survey			X	X	X
Experience and perceptions of intervention materials	Survey					X (CVD-I only)
Engagement with interventions	Achievement website/app and Survey Monkey		[] (CVD-I only)			
Activity tracker data						
Steps	[e.g. Fitbit, Garmin]	X	[]			
Sleep	[e.g. Fitbit, Beddit]	X	[]			
Heart rate	[e.g. Fitbit, Apple]	X	[]			

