#### 8.2.4. Exploratory Analyses

To examine the potential impact of COVID-19 on vaccination rates, we will add a term to the model used in the primary analysis model:

Version 1 18 of 22

$$logit(Y) = \beta_0 + \beta_1 M + \sum_j \beta_j \alpha_j + \beta_c c + \beta_i M * c + \varepsilon$$

Where the additional term c is the Covid-19 status (1 if diagnosed with COVID-19, 0 if not) and the parameter estimate for the interaction term,  $\beta_i$  will be reported. Similarly, we can also evaluate the effect of COVID-19 attitudes towards influenza vaccination rates. In this case, the term c would represent COVID-19 attitudes (1 if the participant reports more likely to vaccinate, 0 if the person does not).

To describe self-reported complications from influenza experienced by individuals with different cardiovascular conditions during the 6-month study period, as well as differences in complications by vaccination status, we will aggregate rates of self-reported complications by cardiovascular conditions, as well as by vaccination status.

To examine differences in wearable data (i.e., sleep, steps, heart rate) between individuals who experience influenza and those who do not, as well as differences in wearable data between cardiovascular conditions, we will aggregate day-level wearable data over the entire study period based on influenza status, as well as by cardiovascular condition.

Between-group comparisons of the outcomes described above (e.g. self reported complications or mean daily steps) will be conducted with Student's t-tests or the non-parametric Mann-Whitney U test when appropriate, with correction for multiple testing using the Benjamini-Hochberg approach for False Discovery Rate correction.

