8.7.2 To examine differences in wearable data (i.e., sleep, steps, heart rate) between individuals who experience influenza and those who do not, as well as differences in wearable data between cardiovascular conditions.

Participants are asked if they were diagnosed with influenza infection in the preceding 3 months for the 3-month and 6-month survey. Differences in daily steps per day, total sleep hours and resting heart rate will be aggregated over the 3 month period and compared among people who report having influenza to those who do not. Similar comparisons within each type of cardiovascular condition will also be performed.

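### The exploratory wearable comparisons pool readings from participants' own trackers without accounting for device make, so a difference in device mix can look like a difference between groups

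*Protocol*

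**What the plan says.** **Source of the data.** Protocol 6.3, repeated under Study Steps in SAP section 5, takes tracker data only from a device the participant already has: "Data from an activity tracker will be collected if one is already connected". The data tables in Protocol section 7 and SAP section 7 give example sources: "e.g. Fitbit, Garmin" for steps, "e.g. Fitbit, Beddit" for sleep and "e.g. Fitbit, Apple" for heart rate. Both documents also plan to collect tracker data from the 12 months before participation, where available.

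**Comparison by influenza status.** In Protocol 8.2.4, "we will aggregate day-level wearable data over the entire study period based on influenza status, as well as by cardiovascular condition". SAP 8.7.2 uses a shorter window: steps, sleep and "resting heart rate will be aggregated over the 3 month period and compared among people who report having influenza" with those who do not.

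**Comparison by condition.** The objective includes "as well as differences in wearable data between cardiovascular conditions" (Protocol 4.3, with the same aim in SAP 3.3 and in the heading of SAP 8.7.2). Protocol 8.2.4 plans this. The method text of SAP 8.7.2 describes only influenza comparisons carried out inside each condition type.

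**Tests and population.** Protocol 8.2.4 and SAP 8.1 both specify Student's t or Mann-Whitney tests, and the Protocol adds a Benjamini-Hochberg correction. Population P3b in SAP 8.2 requires wearable data and consent but sets no condition on the device.

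**The concern.** Two makes may record the same behaviour differently. If so, and if the groups compared differ in which makes their members own, part of the observed difference belongs to the devices. An unadjusted two-sample test cannot separate that part from a difference in activity, sleep or heart rate.

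Only the mix of makes within one measure matters. That different makes are listed for steps than for sleep is harmless, because those measures are never compared with each other.

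The plan has no protection against this. Influenza status and cardiovascular condition are not the randomised arms, so randomisation does not balance device mix between them. The false discovery rate correction deals with multiplicity, not bias. The SAP's one check on tracker data asks whether missingness is associated with the outcome, which says nothing about make. At stake is how the exploratory wearable findings can be read.

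**Working it through.** **1. What can be reproduced.** Nothing numerical. The documents give no sample size, SD, device share or offset between makes for the wearable analysis. The check is therefore of the text, followed by an illustration on assumed values.

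**2. Text.** Neither document has a device covariate, a device stratum, a restriction to one make, a standardisation step or a within-person baseline in the wearable analysis. The earlier 12 months of data are collected, but neither analysis text uses them as a baseline.

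**3. Formulas.**
- Bias = offset between two makes × difference between groups in the share using one of them.
- SE = SD × √(1/n₁ + 1/n₂).
- Rejection rate with no true difference = P(|Z + bias/SE| > 1.96).

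**4. Equal groups, 300 vs 300 (all values assumed).** The share difference is 10 to 30 percentage points.

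| Measure | SD | Offset | Bias | Rejection rate |
|---|---|---|---|---|
| Steps per day | 3,500 | 500 to 1,500 | 50 to 450 | 5.4% to 35% |
| Resting heart rate (bpm) | 10 | 2 to 4 | 0.2 to 1.2 | 5.7% to 31% |
| Sleep (h) | 1.2 | 0.5 | 0.05 to 0.15 (3 to 9 min) | 8% to 33% |

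**5. Unequal groups, as the influenza contrast would be.** Protocol 1.1 gives annual influenza of 5% to 20% in the US population, used here as a stand-in for the share reporting it. Keep 600 people and the largest assumed steps bias, 450.
- 20% report influenza (120 vs 480): SE = 3,500 × √(1/120 + 1/480) = 357; bias/SE = 1.26; rejection rate about 24%.
- 5% report influenza (30 vs 570): SE = 3,500 × √(1/30 + 1/570) = 656; bias/SE = 0.69; rejection rate about 10.5%.
- For comparison, 300 vs 300: SE = 286; bias/SE = 1.57; rejection rate 35%.

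**6. A second set of assumptions, in SD units.** An offset of 0.1 to 0.5 SD and a share difference of 5 to 20 points give a bias of 0.005 to 0.10 SD. The rejection rate is then:
- 5.1% to 35% with 500 vs 500;
- 5.1% to 61% with 1,000 vs 1,000;
- 5.0% to 16% with 100 influenza cases vs 1,900 others.

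The bias does not shrink as the groups grow, so a larger P3b makes a false positive more likely.

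**7. Precision.** A 50:50 mix of two makes adds offset²/4 to the variance. For steps this is 500²/4 ÷ 3,500² = 0.5% up to 1,500²/4 ÷ 3,500² = 4.6%. For heart rate it is 1% to 4%, and for sleep about 4%. Gain in precision is not a reason for the change.

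**The case against.** The strongest reply is that the effect may be absent. The makes are given only as examples, and Fitbit appears for all three measures, so the devices may be nearly uniform within each. The documents give no reason why device make should differ by influenza status. With balanced mix or small offsets, the rates above stay close to 5%. All this stands, and it limits the point to what can happen.

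A reader might infer that false-positive rates of 31% to 35% are to be expected. The documents do not support that. Those rates need the upper assumed bias together with equal groups of 300, and the influenza groups are unlikely to be equal. They are also rates for single uncorrected tests, whereas the Protocol specifies Benjamini-Hochberg correction.

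A reader might also take the between-condition contrast to be settled in both documents. It is in Protocol 8.2.4 and in the objective wording, but not in the SAP 8.7.2 method text.

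Nor do the documents say that device make is stored for each record. That is a plausible inference from connected accounts, not a stated fact.

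Finally, these are non-randomised groups compared without any adjustment, even for age or sex. Accounting for device would remove one source of bias and would not by itself show that a remaining difference is physiological. That too stands.

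**Conclusion.** The point holds as a minor one. Values from participants' own trackers, with more than one make expected per measure, are compared between non-randomised groups by tests that ignore make, so a difference in device mix can appear as a group difference. This applies whether the contrast is by influenza status, within a condition or between conditions.

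Its size cannot be derived from the documents. On assumed offsets, SDs, shares and group sizes it runs from negligible to material, and it is smaller where the groups are unequal. The current plan would not show where this trial falls in that range, because make is not tabulated. The objective is exploratory and carries no power claim.

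**What to change.** In SAP 8.7.2:

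1. For each measure, tabulate device make by influenza status and by condition type. Classify a participant with two devices by the one that supplied that measure.
2. Compare groups with a linear model that has make as a covariate, or with a stratified rank test (van Elteren) where the data are not normal. Pool rare makes as 'other'.
3. Where make is not held in the data, analyse each person's change from their own pre-study tracker data. This cancels a constant device offset if the device is unchanged.
4. Reconcile the method text, which describes comparisons inside each condition, with the objective, which asks for comparisons between conditions.

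The cost is SAP wording and modest programming, with no change to recruitment or surveys. The downsides are a few degrees of freedom, sparse strata for rare makes and, for step 3, losing people who have no earlier data. Steps 1 and 2 assume that make is recorded, which the sponsor must confirm.
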